Our clinic-based studies yielded key findings related to biomarkers, Sound Sweeps performance, and predictors of therapeutic sensitivity to a full course of TCT. **First**, baseline levels of EAIP predicted TCT learning during 1h of Sound Sweeps. **Second**, SZ patients exhibited clinical, neurocognitive and functional gains after 30h of TCT, and changes in EAIP during the first hour of Sound Sweeps testing predicted neurocognitive and clinical gains after a full 30h course of TCT. In total, these findings with memantine, EAIP, TCT learning, and clinical outcomes provide a strong empirical and conceptual framework for a mechanistically-based hypothesis to be tested via the proposed randomized, placebo-controlled 30h pilot trial of (memantine+TCT) vs. (placebo+TCT). Via the below Aims, this application provides efficient pilot testing of this PACT strategy in antipsychotic-medicated SZ patients, using Go/No-Go criteria to inform a future, fully-powered “Confirmatory Efficacy trial”:

AIM 1 – Replicate previous findings of memantine target engagement on TCT learning: In two, 1h tests, determine if memantine increases Sound Sweeps TCT learning in SZ patients (n=54) vs. placebo.

AIM 2 – Test clinical, neurocognitive and functional impact of memantine on TCT, and its relationship to target engagement: In a 30-session course of TCT over 10 weeks, determine if memantine augments the magnitude, rate and/or durability of TCT-induced gains, and whether these gains are associated with target engagement.

AIM 3 – Explore biomarkers of memantine-induced gains: Determine whether higher basal levels of EAIP (and related functional and neurophysiological measures) or changes in these measures across the first hour of Sound Sweeps predict greater sensitivity to memantine-enhanced clinical, neurocognitive or functional gains among SZ patients receiving combined memantine+TCT.

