C. Approach: This application uses an **experimental therapeutics approach** in an "efficient pilot test" of the hypothesis that MEM will augment TCT-induced learning, and thereby clinical, neurocognitive and functional gains, in antipsychotic-medicated SZ patients. In so doing, this application will advance a PACT model for TCT in two specific ways: 1) building on strong preliminary findings, this application will confirm target engagement and identify biomarkers that predict the effectiveness of MEM-enhanced TCT learning, and 2) this application will provide the first randomized controlled trial to assess the ability of medication-enhanced TCT learning (target engagement) to produce significant and lasting clinical, neurocognitive and functional gains in biomarker-characterized SZ patients. In this way, **this application responds to RFA-MH-18-705**, "Development of Psychosocial Therapeutic and Preventive Interventions for Mental Disorders", which supports *"efficient pilot testing of novel psychosocial therapeutic and preventive interventions for mental disorders... using an experimental therapeutics approach."* Moreover, in this application, *"results, whether positive or negative, will provide information of high scientific utility and... support 'go/no-go' decisions about further development or testing of the intervention."* The application uses a *"novel intervention strategy"* - the PACT model - in a design that will *"replicate target engagement and relate change in the... target/mechanism to clinical benefit."* Findings from this pilot study will **inform a future, fully-powered Confirmatory Efficacy trial**.

This application will confirm target engagement by demonstrating that MEM (20 mg po) enhances APS learning in a Sound Sweeps session in biomarker-characterized AP-medicated SZ patients; these patients will then be randomized to a 30-session RCT of TCT+MEM (n=27) vs. TCT+PBO (n=27). Findings will determine whether MEM augments the known neurocognitive and clinical benefits of TCT, and whether APS "MEM sensitivity" - based on APS gains in 2 test sessions - predicts the therapeutic impact of MEM over a 30-session TCT regimen. Other predictive biomarkers will be explored, including baseline neurocognitive (MCCB scores), ERP (MMN, P3a) / EEG (ASSR, evoked theta band power) measures, and MEM effects on auditory discrimination and on ERP changes across the first Sound Sweeps sessions.

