Outcome and “Go Decisions”. In addition to confirming “target engagement”, this application tests the hypothesis that SZ patients given MEM +TCT will exhibit greater, faster and/or more durable improvements (change from baseline) in symptoms, neurocognition and/or function compared to patients given PBO+TCT, and that this enhanced clinical response will be associated with greater MEM-enhanced TCT learning.

The small “n” necessitated by the 3-year timeline and demanding treatment schedule greatly constrains the total number of outcome measures.

Moreover, the plan to assess not only magnitude but also rate and durability of PACT gains triples the number of primary analyses. Thus, we selected only one **primary** clinical, neurocognitive and functional outcome measure (Table 1) – recognizing that they are relatively “blunt” metrics - but will track several other, more focused, measures as well as inter-measure correlations in exploratory analyses to inform future studies.

A “Go” decision requires: 1) confirmation of target engagement (APS learning, MEM>PBO, p<0.05); 2) evidence of gains from PACT ($d \geq 0.5$ (MEM > PBO)) in primary clinical, neurocognitive and/or functional measures (Table 1), and 3) the absence of adverse effects of MEM that are significantly greater than PBO levels. The decision to not use traditional statistical significance as “Go” criteria for Aim 2 reflects this RFA’s call for “Pilot” studies, the need to identify candidate treatments for a subsequent larger “n” Confirmatory Efficacy R01 study, and the limits in sample size resulting from the 3-year R33 duration. Cohen defined a medium effect size ($d=0.5$) as one that is “visible to the naked eye,” and this amount of change is viewed as clinically meaningful in trials targeting negative symptoms.⁹⁹⁻¹⁰¹ This $d=0.5$ “Go” threshold for Aim 2 corresponds to a “number needed to treat” (NNT) value ≈ 3.62 . While a “Go” decision does not require identification of a biomarker predicting greater PACT sensitivity (Aim 3), the identification of one or more meaningful predictors that could be incorporated into a Confirmatory Efficacy trial would favorably impact a “Go” decision.

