Neurocognition: Change in MCCB Composite performance from baseline is one outcome measure. The MCCB measures 7 cognitive domains: speed of processing, attention/vigilance, working memory (verbal and nonverbal), verbal learning, visual learning, reasoning/ problem solving and social cognition. Details are found in^{36,102,103}; past studies of drug effects on MCCB performance include^{48,104}. Since the MCCB is assessed multiple times, alternate forms of the HVLT-R and BVMT-R are used in counterbalanced order. **MCCB Global Composite T-score (MCCB-C) is the primary neurocognitive outcome measure**. Individual MCCB domain T-scores are used in secondary analyses to determine whether an overall effect is driven by specific aspects of neurocognition; TCT effects on verbal learning performance are known to be robust²⁴, and should be augmented by MEM. Baseline and MEM-enhanced (Test 2 vs. 1) MCCB performance (A/V subscale) will also be tested as potential biomarkers/moderators of MEM PACT efficacy.

Function is assessed via the World Health Organization Disability Schedule 2.0 (WHODAS)¹⁰⁵ at baseline, after sessions 10, 20 and 30, and week 12 post-TCT. WHODAS 2.0 is a 12-item patient-rated measure (< 15 min) using a 5-point Likert scale focusing on cognition, mobility, self-care, getting along with people, life activities and participating in society; it was selected by the DSM-5 Task Force committee to replace the global assessment of functioning scale¹⁰⁶. **NIH “PhenX Toolkit”** scales of Impairment, QOL and Social Isolation will also be used. After session #30, the assessment will include a 14-item 7-point Likert scale of treatment satisfaction.

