Aim 1 – Confirm target engagement: The primary dependent measure of target engagement is MEM-enhanced APS learning. APS learning is defined as the reduction in Sound Sweeps APS threshold (ms) Test 1 to Test 2 assessment. Target engagement was demonstrated in Fig. 3⁷⁶, and will be confirmed if APS learning is increased by MEM (note that MEM and PBO groups are matched by Test 1 PBO performance via stratified randomized assignment). As appropriate, effect sizes and inferential statistics are based on standard regression or LME models with random intercepts. A significant interaction between contrast coded drug (PBO vs. MEM) and Test (Test 1 vs. Test 2) predictors on APS learning is a “Go” criteria and confirms target engagement.

Aim 2 – Test clinical, neurocognitive and functional impact of MEM on TCT, and its relationship to target engagement: We will determine if MEM+TCT produces greater, faster or more durable clinical, neurocognitive or functional gains from baseline, compared to PBO+TCT, over a 30-session course of TCT. A Cohen’s $d > 0.5$ for the main effect of drug (PBO vs. MEM) or drug x session (#10, 20, 30) interaction in an LME model is the primary “Go” criteria. The effect of drug assesses “greater” gains. Reverse Helmert contrasts for session assesses “faster” gains. A separate model comparing differences in outcomes at 12-weeks post-TCT assesses “more durable” gains. Secondary analyses will examine whether change in MEM-enhanced APS learning (“within-subject” target engagement; Aim 1) predicts gains in Aim 2 outcome measures.

Aim 3 – Biomarkers of MEM-induced gains: We will determine if baseline levels of specific neurocognitive or EEG-based measures, or changes in specific measures with initial MEM exposure (Test 2 vs. 1), predict greater sensitivity to MEM-enhanced neurocognitive, clinical or functional gains over 30-h of TCT. Regression analyses will assess whether specific candidate biomarkers predict MEM-enhanced gains in outcome measures.

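### Unless Aim 3 specifies a drug-by-marker test, regressing MCCB gain on MCCB-derived markers will find predictors too often, because marker and gain share baseline error

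*Combined protocol and SAP*

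**What the plan says.** - **Outcome.** Research Strategy, C. Approach, Neurocognition: "Change in MCCB Composite performance from baseline is one outcome measure". The composite T-score is the primary neurocognitive measure, and A/V is one of seven domains. The domains are also analysed: "Individual MCCB domain T-scores are used in secondary analyses to determine whether an overall effect is driven by specific aspects of neurocognition".
- **Markers.** The same paragraph says: "Baseline and MEM-enhanced (Test 2 vs. 1) MCCB performance (A/V subscale) will also be tested as potential biomarkers/moderators of MEM PACT efficacy". The Biomarkers paragraph repeats the A/V markers. The opening of C. Approach is wider: "Other predictive biomarkers will be explored, including baseline neurocognitive (MCCB scores" are listed there without restriction to A/V.
- **Analysis.** Data Analysis, Aim 3: "Regression analyses will assess whether specific candidate biomarkers predict MEM-enhanced gains in outcome measures". No equation, covariate or interaction term is given. Specific Aims, Aim 3, asks whether the markers "predict greater sensitivity to memantine-enhanced clinical, neurocognitive or functional gains among SZ patients receiving combined memantine+TCT".
- **Safeguards.** Data Analysis recognises that outcomes are changes from baseline, but deals only with baseline differences between arms. Tests are two-sided at 0.05, with false discovery rate correction for secondary analyses.
- **Use.** Outcome and Go Decisions says that a Go does not depend on finding a biomarker, but that "the identification of one or more meaningful predictors that could be incorporated into a Confirmatory Efficacy trial would favorably impact" the decision.

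**The concern.** A patient who scores low at baseline by chance has a low baseline marker and, on retest, an apparent gain. Error that enters the marker with a plus sign enters the gain with a minus sign, so the slope is negative with no biology behind it. For the Test 2 minus Test 1 A/V change the sign reverses: if Test 1 supplies the baseline A/V score, marker and gain both subtract the same number. The spurious slope is then positive, which is the direction the investigators hope to see.

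In neither case is zero the right reference value for the slope. False discovery rate control takes the p-values as valid, so it cannot repair them. EEG, speech-in-noise and Sound Sweeps markers of MCCB gain do not share this error, so MCCB markers could look better than those for an artificial reason. A marker chosen this way could favour a Go and be built into the confirmatory trial.

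**Working it through.** **The plan's own figures.** The documents give no power or error rate for Aim 3. The only sample-size figure is for Aim 1 (d=0.5, retest correlation 0.8, 80% power). It reproduces: the SD of a change score is sqrt(2 x (1 - 0.8)) = 0.632, and a t-based calculation gives 79.8% power at 26 per group and 81.4% at 27. It does not bear on Aim 3.

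**Inputs from the documents.** Seven domains; two-sided 0.05; 27 randomised per arm; conservatively 18 completers per arm (Subject throughput).

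**Assumptions, since the documents give no values.** Equal domain weights; domain variance 1; reliability R = 0.7 to 0.8; true-score covariance between domains s = 0.3 to 0.4; errors independent across domains and visits; no drug or marker effect; for the Test 2 minus Test 1 marker, Test 1 A/V is the baseline A/V.

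**Null correlations.** With no variation in true change, composite gain has variance 2(1-R)/7.

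1. Baseline A/V: covariance -(1-R)/7, marker variance 1, so rho = -sqrt((1-R)/14). This is -0.12 at R=0.8 and -0.15 at R=0.7.
2. Baseline composite: marker variance (1+6s)/7, so rho = -sqrt((1-R)/(2(1+6s))). This is -0.17 at R=0.8, s=0.4 and -0.23 at R=0.7, s=0.3.
3. Test 2 minus Test 1 A/V: covariance +(1-R)/7, marker variance 2(1-R), so rho = 1/(2 sqrt(7)) = 0.19 for any R.

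If true change varies between patients with SD 0.3, common to all domains, the gain variance rises by 0.09. At R=0.8 it goes from 0.057 to 0.147, and the correlations (s=0.4 for the composite) shrink to -0.07, -0.11 and 0.12.

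If 5% of total variance is same-day error shared across domains (R=0.8), the third covariance is 0.05 + 0.15/7 = 0.0714 and the gain variance is 0.1429. Then rho = 0.0714/sqrt(0.4 x 0.1429) = 0.30.

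**False-positive rates.** By Fisher's approximation, delta = atanh(|rho|) x sqrt(n-3) and rate = Phi(-1.96+delta) + Phi(-1.96-delta). Example: rho = 0.1195, n=18 gives delta = 0.1201 x 3.873 = 0.465, and the rate is 0.0675 + 0.0077 = 7.5%.

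| Marker against composite gain, memantine arm | n=18 | n=27 |
|---|---|---|
| Baseline A/V, R=0.8 / R=0.7 | 7.5% / 8.8% | 9.0% / 11.2% |
| Baseline A/V, R=0.8, true-change SD 0.3 | 6.0% | 6.5% |
| Baseline composite, R=0.8, s=0.4 / R=0.7, s=0.3 | 10.3% / 15.0% | 13.6% / 21.1% |
| Baseline composite, R=0.8, s=0.4, true-change SD 0.3 | 7.0% | 8.2% |
| Test 2-1 A/V, any R | 11.5% | 15.5% |
| Test 2-1 A/V, R=0.8, true-change SD 0.3 | 7.4% | 8.9% |
| Test 2-1 A/V, R=0.8, 5% shared same-day error | 22.3% | 32.7% |

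Null simulations agree to within about one percentage point. For example, at R=0.8 and n=18/27 they give 7.7%/9.2% for baseline A/V, 10.3%/13.4% for the baseline composite and 12.2%/15.8% for Test 2-1 A/V. Pooling the arms makes it worse because n doubles: with independent errors and R = 0.7 to 0.8, the Test 2-1 marker rejects in 10 to 20% of trials at 36 patients and 13 to 27% at 54.

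**Remedies under the same null.**

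- The drug x marker term rejects in 4.6 to 5.8% of simulated trials, because the expected artefact slope is the same in both arms and cancels.
- With the baseline composite as covariate, baseline A/V returns to 4.7 to 5.6%. The Test 2-1 marker stays at 9 to 54%, the top of that range coming from scenarios with substantial shared same-day error.
- With the six-domain composite as outcome, A/V markers reject at about 5% when errors are independent. With 5% shared same-day error the Test 2-1 marker still rejects in about 18% at n=27.

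**The case against.** The strongest reply is that the plan writes down no zero-slope test. The sentence naming the A/V markers also calls them moderators, and Aim 3 concerns memantine-enhanced gains. Read as a drug x marker interaction, the error rate is nominal and the problem disappears. That stands: a reader might infer that the plan commits to a biased test, and it does not. But it does not commit to the unbiased one either. Specific Aims places the question among patients receiving memantine, and the Biomarkers and Power analyses paragraphs leave formal moderator modelling to a later trial.

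Second, A/V is one domain of seven, so baseline A/V shares only part of the composite's error and the inflation is modest. That stands. The larger baseline figures apply only to the composite as its own predictor, which rests on the broader mention of MCCB scores in C. Approach.

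Third, the Test 2-1 result requires Test 1 A/V to be the baseline score. The Design paragraph labels Test 1 as baseline with reference to Sound Sweeps learning, while Section 4.2.a lists the neurocognitive measures ahead of the two tests. The documents do not settle it. If the administrations are separate, this part vanishes.

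Fourth, a much more alarming number is within reach. Regressing A/V's own gain on Test 2-1 A/V has null rho = 0.5 and rejects in roughly 59% of trials at n=18 and 78% at n=27. No section names that regression, so these rates should not be charged to the plan.

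Finally, the interaction test is weak here. At 18 per arm the standard error of a Fisher-z difference is sqrt(2/15) = 0.365, so 80% power needs about r = 0.77 against 0. For r = 0.58 (the size reported for P3a under Predictors of gains) against 0, power is about 44%. That stands as a cost, but a weak valid test is preferable to a stronger one with the wrong reference value.

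**Conclusion.** The concern holds conditionally. If Aim 3 is run as a within-arm or pooled slope, MCCB-derived markers of MCCB gain are declared predictive more often than 5% when they are irrelevant. With R = 0.7 to 0.8 and independent errors, the memantine-arm rates at n=18 and n=27 are about 6 to 9% and 7 to 11% for baseline A/V, and 7 to 15% and 8 to 21% for the baseline composite. If Test 1 is the baseline administration, they are 7 to 12% and 9 to 16% for Test 2-1 A/V. The low ends assume a true-change SD of 0.3. A 5% shared same-day error takes the Test 2-1 rates to about 23% and 33%.

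A reader might conclude that the Go decision itself is compromised. The documents do not support that: no biomarker is required for a Go, Table 1 contains none, and PANSS and WHODAS gains carry no MCCB error. What is exposed is a secondary analysis that may tilt a Go and shape the next trial. The plan should be amended, but the primary analyses do not depend on it.

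**What to change.** Add to Data Analysis, Aim 3, a rule for MCCB-derived markers of MCCB gain:

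1. Test the drug x marker term using both arms, and count a marker as predictive only on that term.
2. When A/V (baseline or Test 2-1) is the marker, use the composite without A/V as the outcome, and do not use A/V markers for A/V gain. This alone is not enough if same-day error is shared across domains, so step 1 is still needed.
3. Label single-arm or pooled slopes of MCCB change on an MCCB score as descriptive, with no bearing on the Go decision.

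For baseline A/V, adjusting for the baseline composite is an acceptable alternative. It does not repair the Test 2-1 marker. The plan should also state whether Test 1 A/V is the baseline administration.

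Cost: wording and one derived score, with no new data. The slope contrast is less precise than a single slope, and the six-domain composite is slightly less reliable than the full one. Test 2 follows assignment, so Test 2-1 A/V is not a true baseline moderator. If acute drug response varies between patients (assumed SD 0.5), its interaction test rejects in about 6 to 7% of simulated trials. That contrast should be reported with this caveat.

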General Methods: Environment: Subjects are screened, tested and undergo TCT at the UCSD Medical Center. Participants are 18-55 y.o. AP-medicated (stable regimen \geq 1 month, in active outpatient treatment) patients with a primary diagnosis of SZ or schizoaffective disorder (depressed type), recruited and consented at UCSD as per^{49,59,74}. Study inclusion/exclusion criteria are detailed in "**Protection of Human Subjects**". Screening includes a confirmatory diagnostic assessment (M.I.N.I. 6.0), a general medical, psychiatric and substance history, physical exam by an M.D., EKG, vision and hearing tests, urine toxicology and pregnancy test (UTox/P). All medications and changes are recorded (AP doses in chlorpromazine equivalents; quantifying anticholinergic burden⁹⁵ as in^{33,48,49}). Medication patterns of our last \approx 100 SZ subjects are published elsewhere^{49,74,96}.

Design (Fig. 5). Enrolled patients complete clinical, neurocognitive and functional measures and candidate biomarkers (EEG, QuickSIN, WIN) tested in Sound Sweeps at baseline, and then assigned to PBO vs. MEM arms (n=27/arm) using stratified random sampling (over sex, age and high/low Test 1 (baseline) APS learning) blind to arm identity. Stratifying for baseline APS learning should increase the sensitivity of the primary target engagement metric. Test 2 follows \approx 5-7 days later, after either PBO or MEM (20 mg po). Tests 1-2 are used to assess target engagement (Aim 1: MEM-enhanced APS learning) as well as MEM effects on ERP/EEG, auditory discrimination (QuickSIN, WIN) and neurocognitive measures (Aim 3: Biomarkers). Our design allows for 20% attrition from enrollment (n=69) to completion of target engagement testing (n=54).

For Aim 2, all participants will be titrated up to 20 mg MEM or Placebo over a 3-week period and concurrently begin TCT 3 d/week (M-W-F) for 1-h/d (recognizing the need for flexibility, T-Th are "make-up days"), and continues until a subject completes 30-h (\approx 10-12 weeks). TCT is delivered by trained staff (see below). Patients and staff are blind to study arm; staff are blind to patients' baseline, interval, and post-intervention assessments.

[figure not shown]

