Subject “throughput”: We will enroll and screen 23 subjects/yr, test target engagement in 18 subjects/yr, and (conservatively) complete TCT training in 12 subjects/yr. This will yield 2 “target engagement” Aim 1 arms of n=27, and (conservatively) 2 TCT completion Aim 2 arms of n=18. Training capacity (2 TCT stations with morning and afternoon sessions on M, W and F, with T and Th “make-up” days for missed appointments, 48 weeks/year) allows for a “maximum throughput” of 19.2 subjects/yr. To reach the target of **12 TCT-completing subjects/year**, we would need to maintain training rates of **62.5% capacity**. This is well within our historical testing levels.

Power analyses: Consistent with the FOA, this study will adequately power tests of target engagement (Aim 1) for traditional significance, while the “Go” signal for therapeutic impact (Aim 2) is based on effect size ($d=0.5$). To detect target engagement for an LME model with $d=0.5$, 80% power, alpha=0.05, test-retest correlation=0.8, and a linear treatment effect, n=27 randomized participants are required per Hedeker et al (1999). This is a conservative estimate of d for target engagement, since empirically, d for target engagement with 20 mg MEM was 0.85 (Fig. 3). A future Confirmatory Efficacy trial will be powered to apply more robust approaches to Aim 2, e.g. Path Analysis⁶⁰ to study moderating effects of APS MEM sensitivity and biomarkers on both indirect (moderated-mediation) and direct paths between treatment and outcome.

Innovative ideas raise questions. Here are some answers:

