Differential drop-out rates from PBO vs. MEM arms are monitored. Clinical follow-up is pursued with all patients exiting the study through post-TCT week 12.

Cohort differences: For between-subject contrasts (drug), baseline demographic, clinical, antipsychotic/anticholinergic load and performance differences are tested and used as covariates if indicated. Sex differences are tested for all measures.

Procedures for Alternative or Unexpected Results: Linear mixed-effects models allow for the analysis of all available data using an intent-to-treat approach. This approach, however, assumes that data are missing at random. A potential concern is nonrandom dropout, particularly when dropout is related to the (missing) outcomes; that is, not missing at random. To make the missing at random assumption more plausible, we will explore the use of auxiliary variables. Auxiliary variables are covariates that predict both dropout and outcomes. By adding

auxiliary variables to our models, nonrandom dropout is corrected by conditioning treatment effects on the predictors of dropout.

Primary Efficacy Endpoint(s): Aim 1: Target engagement – APS learning will be significantly greater under MEM vs. PBO conditions. Aim 2: Pilot trial - Compared to PBO arm patients, MEM arm patients will exhibit greater clinical benefit, as indicated by one or more of the following: greater, faster or more durable improvements in PANSSt (reduced scores; see below, "Go/No-Go"), MCCBc (increased scores) or WHODAS (reduced scores).

Secondary Efficacy Endpoint(s): Aim 3: Biomarkers - baseline levels of specific neurocognitive or EEG-based measures, or changes in specific measures with initial MEM exposure, predict greater sensitivity to MEM-enhanced neurocognitive, clinical or functional gains over 30 sessions of TCT.

Analyses testing primary and secondary hypotheses will include all subjects' clinical, neurocognitive and functional assessments. Data from subjects who do not complete the full study are carried forward in an "intent to treat" design, and their data are analyzed using linear mixed models. Separate analyses will compare completion / drop-out rates across arms, as well as a 14-item 7-point Likert scale assessing treatment satisfaction.

Go/No-Go decision and primary and secondary endpoints

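### Treatment satisfaction is to be compared between arms but is asked only after session 30, so as scheduled the comparison covers training completers only

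*Combined protocol and SAP*

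**What the plan says.** The Function paragraph of the Research Strategy (Approach) sets the timing: "After session #30, the assessment will include a 14-item 7-point Likert scale of treatment satisfaction". The WHODAS row of section 4.3 repeats it. Neither place, nor any other, schedules the scale at baseline, at sessions 10 or 20, on early exit, or at follow-up.

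Section 4.4 sets the analysis: "Separate analyses will compare completion / drop-out rates across arms, as well as a 14-item 7-point Likert scale assessing treatment satisfaction". The natural reading is that both items are compared between arms.

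The throughput paragraph gives the expected numbers: "test target engagement in 18 subjects/yr", and then "conservatively) 2 TCT completion Aim 2 arms of n=18".

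The Data Analysis paragraph and section 4.4 also provide for clinical follow-up of patients who leave, to 12 weeks after training. They allow full information maximum likelihood, section 4.4 adds multiple imputation, and it says that auxiliary variables will be explored. No text connects any of these to the satisfaction scale.

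**The concern.** A measure taken only at the end of training exists only for those who reach the end. The planned comparison is therefore between two groups of completers and not between the randomised arms. Dissatisfaction is a plausible reason for stopping, so the missing scores may be the most informative ones.

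This matters for what the pilot is meant to deliver. It is to inform a confirmatory trial, and its Significance section concedes that the burden of getting severely ill patients through even 30 hours of training can be a serious obstacle. How acceptable the treatment was to those who stopped is useful for planning the next trial. If it is not asked at the time, no later analysis can recover it.

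**Working it through.** **1. Reproduce the plan's figure.** The throughput paragraph gives 18 patients per year tested for target engagement and 12 per year completing training. The timeline is 3 years with two arms.

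- Tested: 18 × 3 = 54, or 27 per arm.
- Completing: 12 × 3 = 36, or 18 per arm, as the plan states.
- With a scheduled score: 36/54 = 66.7%. Without: 18/54 = 33.3%.

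The plan calls the completion figure conservative. If the loss were 10% or 20% (assumed), 27 × 0.9 = 24.3 or 27 × 0.8 = 21.6 per arm would be scored.

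**2. What the missing-data methods can use.** PANSS, MCCB and WHODAS are measured at baseline and after sessions 10 and 20, so a patient who stops early may still contribute earlier values of the same measure. Satisfaction has no earlier value. A likelihood analysis of the scale alone gains nothing from a patient with no score. Multiple imputation would have to predict it from other variables, and the plan names none for this purpose.

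**3. Size of a possible distortion.** The documents give neither drop-out by arm nor the link between satisfaction and staying, so both are assumptions here. Let satisfaction and the tendency to stay be bivariate normal with correlation ρ, and let p be an arm's drop-out proportion. Then:

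- overstatement of mean satisfaction among completers = ρ·φ(z(p))/(1 − p), in SD units, where z(p) is the normal quantile and φ the normal density;
- arm bias with no true difference = the value in the arm with more drop-out minus the value in the other.

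Example with ρ = 0.5 and 6 vs 12 of 27 lost:

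- p = 6/27: 0.5 × 0.298/0.778 = 0.191.
- p = 12/27: 0.5 × 0.395/0.556 = 0.356.
- Bias, from unrounded values = 0.164 SD.

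Holding the total loss at 18 of 54, the spurious advantage of the arm with more drop-out (SD) is:

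| Lost per arm | ρ = 0.2 | ρ = 0.3 | ρ = 0.5 |
|---|---|---|---|
| 9 vs 9 | 0 | 0 | 0 |
| 8 vs 10 | 0.02 | 0.03 | 0.05 |
| 6 vs 12 | 0.07 | 0.10 | 0.16 |
| 4 vs 14 | 0.11 | 0.17 | 0.28 |

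With ρ = 0 every entry is zero; with negative ρ the sign reverses. With 9 vs 9 lost there is no arm bias, but mean satisfaction is overstated in both arms by 0.11, 0.16 or 0.27 SD at ρ = 0.2, 0.3 or 0.5.

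**4. Scale.** With 18 per arm the standard error of a difference is √(2/18) = 0.33 SD. Even the largest entry, 0.28 SD, is below one standard error.

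**The case against.** The case against runs as follows.

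- **The one-third loss is a planning floor.** A reader might infer that a third of patients are expected to stop. The documents do not say so: the figure is a conservative throughput assumption. The Assessments paragraph reports that 90% of earlier subjects finished 30 sessions within 11 weeks, which hints at a smaller loss, although its denominator is not given. This stands, and the loss should be worded as up to about one third.
- **The direction of bias is not established.** A reader might infer that the arm with more drop-out will look more satisfied, or that memantine will be flattered. That needs unequal drop-out and also dissatisfied patients leaving more often. The documents show neither. The meta-analysis cited for memantine (15 trials, 512 patients) reports no excess discontinuation, though none of those trials included cognitive training. This stands; the bias is conditional.
- **Missing data are not ignored.** Multiple imputation and auxiliary variables are allowed. This stands as far as it goes, but without an earlier score such imputation would be weak.
- **An imbalance would be seen.** Drop-out is compared across arms in the same sentence as satisfaction. This also stands, but seeing an imbalance does not correct the satisfaction comparison.
- **Leaving is not the same as being dissatisfied.** Three positive toxicology tests end participation. This is a sound reason not to score everyone who stops as least satisfied.

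None of this changes the fact that the scale is scheduled for completers only.

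**Conclusion.** The point holds as a limited design gap. As written, the arm comparison of satisfaction is a completers-only comparison, and on the plan's conservative figure up to 18 of 54 patients would have no score. That part rests on the schedule and needs no assumption about why patients leave.

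The bias is conditional. It is about 0.02 to 0.28 SD in favour of the arm with more drop-out under the correlations and splits shown, and zero if drop-out is equal or unrelated to satisfaction. Overstatement in both arms needs only that dissatisfied patients leave more often.

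The consequence is small. Satisfaction is not a primary outcome, not part of the Aim 3 secondary endpoint and not a Go criterion. A reader might infer that the Go decision or the main efficacy results are at risk; the documents do not support that.

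**What to change.** In the Function paragraph and in the WHODAS row of section 4.3, schedule the scale after session 30 or when the patient stops training, whichever comes first. For patients who stop, use the follow-up contact already planned in the Data Analysis paragraph.

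In section 4.4, state that arms are compared in all randomised patients with a completed scale, that completers and early stoppers are also shown separately, and that any comparison restricted to session-30 scores is labelled completers-only.

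The cost is one 14-item questionnaire for about 18 patients on the plan's conservative figure, plus a few sentences of text. Scored patients could rise from 36 to as many as 54. The drawback is that an exit score reflects fewer sessions than a session-30 score; the separate display deals with that. If exit collection is not feasible, the label alone would prevent misreading.
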